Study Population. Our clinical population will be men and women (N=5 to 7) 21-60 years old who are currently living with HIV (under antiretroviral therapy for 5+ years with a suppressed viral load).

Recruitment strategy. Co-I [name] has extensive experience in HIV patient recruitment and will oversee the recruitment team, during the recruitment phase, as well as the safety monitoring. Five PLWH (men and women) will be primarily recruited from The SHARC Registry (IRB# 201400073), a UF-IRB-approved registry of over 600 HIV patients who have agreed to be contacted about future research. Written informed consent will be obtained, and blood will be collected at the UF CTRB clinical research center. Inclusion criteria are: ability to read English and provide written consent; willingness to take CBD and to participate in follow up for two months; older than 21 and younger than 60; under antiretroviral therapy for 5+ years and suppressed viral load (CD4 count <350cells/ml); patients must agree to practice acceptable methods of birth control, namely sterilization (female tubal ligation or occlusion, male vasectomy), long-acting reversible contraceptives (intrauterine devices, hormonal implants), short-acting hormonal methods (pill, mini pills, patch, shot, vaginal ring), and condoms.

The main exclusion criterion will be conditions/medications that may impair the immune response (e.g. rheumatoid arthritis, cancer, diabetes chronic infections, CAD, cellulitis, autoimmune diseases such as lupus, sarcoidosis, and all medications they may affect inflammation such as aspirin, steroids, statins);), pregnancy, and current marijuana or CBD use (urine drug screen). Further exclusion criteria will be: excluding subjects taking anti-seizure medicines, with any history of seizure disorder or head trauma, any history of hepatic/liver disease or renal disease, any history of cardiovascular diseases; women who are lactating (in addition to existing exclusion criteria for pregnancy). Co-I [name] (a physician) will review conditions/medications after the initial interview before the patient is enrolled to exclude risks of drug interactions or hepatotoxicity. UF/Shands staff and students will not be considered for enrollment. Presence of chronic pain will not be considered as a necessary condition for enrollment.

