Motivation to study single cells. The molecular and cellular changes underlying the inflammation mitigation caused by CBD-administration are largely unknown, and stand as a major challenge both for understanding its basic biology (e.g., pathways involved, molecular mechanisms) and for the urgent unmet need of reducing the long-term harm chronic inflammation causes in PLWH. Our hypothesis is that CBD alters monocyte migration capacity with MAPK-dependent alterations. We expect this alteration to have

chain-effects based on cellular cross-talk, i.e., that different PBMC cell types (such as Tcells and B-cells) might express specific CBD-induced phenotypes. We hypothesize CBD-alterations to reverberate along the whole immune-modulation system through cellular cross-talk. Given the complexity of the immune response, we deem traditional (bulk) RNA sequencing as insufficient for the task. Population-averaged genomic profiling cannot adequately unravel the inter-cellular regulation in situ. This study will leverage the efficiency of newly available single-cell technologies to create a powerful dataset unveiling the functional properties of thousands of individual cells.

Sample collection and processing. We plan to collect samples from five to seven patients over three time points: baseline (no CBD), and after one and two months of CBD-administration with 5,000 cells sequenced per sample. Five to seven patients (15 to 21 samples) will provide the transcriptomes of 75,000-105,000 single cells, a large dataset for scRNAseq. Immediately after collection, samples will be collected by TBD Lab technician to be processed for scRNAseq at UF ICBR (PBMC scRNAseq experiments are routinely run at ICBR).

Data analysis. During the post-processing period, single-cell reads (count matrices) will be filtered for quality control. Unsupervised clustering will isolate statistically robust populations of similar cells. Clusters will be visualized using Principal Component Analysis (PCA), t-Distributed Stochastic Neighbor Embedding (tSNE), and Uniform Manifold Approximation and Projection (UMAP). The most informative gene expression markers will be identified by a host of non-parametric tests (e.g., the Kolmogorov–Smirnov test), comparing a given cluster against either a nearby cluster or all other clusters. Clusters of cells will be annotated by using their marker genes/pathways⁻ and prior biological knowledge to characterize each sample's cell composition.

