Primary Outcomes: This study takes a single-cell perspective, i.e., we will collect a large number of cells from a small number of patients, and we will measure RNA expression per single cell (not per patient). Note that from the single cell point of view, the number of patients (5-7) is sufficient to derive statistically viable results, as we will collect 5,000 cells from each patient at each time point (total 75,000-105,000 cells). Each cell will be sequence individually to read the RNA expression from a panel of approximately 20,000 genes. Cells will be pooled from all patients, and clustered via unsupervised algorithms into clusters of different cell types (e.g. T cells, B cells, monocytes). Our primary outcomes will be the extraction of gene expression patterns (RNA) from specific immune cell types found in PBMC (e.g., B cells, T cells, monocytes). We will regress these gene markers against the variation in baseline inflammation (C-reactive protein, erythrocyte sedimentation rate, and procalcitonin). After CBD administration to obtain CBD-related biomarkers for inflammation reduction. The difference in gene expression will be measured in fold change, p-value, and ratio of cell fraction expressing the marker gene. These biomarker gene will be unique for each cell type. We expect to extract specific biomarkers for each cell type and understand how CBD alters gene expressions of different immune cells in a different way-overall, we expect the genes of the MAPK signaling pathway (MAPK families play an important role in complex cellular programs like proliferation, differentiation, development, transformation, and apoptosis) to be strongly altered.

Secondary Outcomes. Self-report pain ratings will be used to determine peak pain intensity and pain persistence. The brief pain inventory (BPI) will be used to self-report pain perception. The inventory consists of rating pain on a visual analog scale (VAS). A 10cm line is drawn with 0 (no pain) on the left pole and 10 (worst pain imaginable) on the right pole. The inventory asks participants to rate their level of pain by placing a slash on the line that best represents their current level of pain as well as pain at its worst, best and average over the past 24 hours. The highest worst pain intensity reported during the intervention will be recorded as the peak pain intensity.

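### The regression of gene markers on CRP, ESR and procalcitonin has only 5–7 patients' marker values behind it; cells cannot replace them, and the unit of analysis and model form are not stated

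*Combined protocol and SAP*

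**What the plan says.** In section 6 (Research Plan), Primary Outcomes, cells are pooled over patients and clustered into cell types, and expression patterns are extracted for each type. Then: "We will regress these gene markers against the variation in baseline inflammation (C-reactive protein, erythrocyte sedimentation rate, and procalcitonin". The next sentence is a fragment about obtaining CBD-related biomarkers after administration, so the intended contrast is unclear.

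On the unit of analysis, the same section says "we will measure RNA expression per single cell (not per patient". On size it says "Note that from the single cell point of view, the number of patients (5-7) is sufficient to derive statistically viable results", because "we will collect 5,000 cells from each patient at each time point (total 75,000-105,000 cells". On breadth: "Each cell will be sequence individually to read the RNA expression from a panel of approximately 20,000 genes".

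Study Population gives "men and women (N=5 to 7) 21-60 years old", while Specific Aims speaks of five persons. Sample collection and processing states: "We plan to collect samples from five to seven patients over three time points".

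The plan does not state:
- whether the markers enter together or singly;
- whether rows are cells, samples or patients;
- whether a patient effect is fitted;
- which visits are used;
- which significance level or multiplicity rule applies.

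The visit lists under Experimental Procedures name a blood draw at each visit but do not name the three assays.

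**The concern.** This step is what links genes that change under CBD to inflammation, and so turns them into candidate biomarkers of inflammation reduction. The cell count is offered as the reason why 5–7 patients suffice. It is not relevant to this regression: all cells from one draw share one CRP, one ESR and one procalcitonin value. The independent information on the predictor side is 5–7 values per marker per contrast, however many cells are sequenced.

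An analyst following the text could treat cells as independent and get p-values that are far too small. The same analyst could instead fit three predictors to 5–7 patients with very little power, or test three markers and report whichever passes. Possible Benefits says that the data may be used to plan a larger trial, so a wrong candidate list could be carried forward.

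**Working it through.** **Inputs from the documents.** Patients n = 5 to 7; 3 time points; 5,000 cells per patient per time point; 3 markers; about 20,000 genes. **Assumed, because not stated:** two-sided 5% level; intra-patient correlation (ICC) of expression 0.01–0.10; marker-to-inflammation correlation 0.8; gene-to-inflammation correlation 0.5–0.9.

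**1. The plan's own figure.** 5 × 3 × 5,000 = 75,000 and 7 × 3 × 5,000 = 105,000 cells, from 15 and 21 samples. This reproduces. Marker values at one draw: 5 to 7 per marker.

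**2. Rows are cells, no patient effect.** With m cells per patient sharing one marker value, the true variance of a slope is about DE = 1 + (m − 1) × ICC times the variance that the naive fit reports. The false-positive rate is about P(|Z| > 1.96/√DE).

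| m | ICC | DE | 1.96/√DE | False positives per marker |
|---|---|---|---|---|
| 5,000 | 0.01 | 51.0 | 0.274 | 78% |
| 5,000 | 0.05 | 251 | 0.124 | 90% |
| 5,000 | 0.10 | 501 | 0.088 | 93% |
| 500 | 0.01 | 6.0 | 0.801 | 42% |
| 500 | 0.10 | 50.9 | 0.275 | 78% |

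Simulation with three markers (20,000 runs) gives the same picture: 78%, 90–91% and 93% with 5,000 cells, and 42% to 79% with 500. The rate is 5% only if ICC is zero. The 5,000 cells cover all cell types, so the 500-cell rows show a smaller cell type.

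**3. Rows are patients, three markers jointly, one contrast.** Residual df = n − 3 − 1 = 1, 2, 3 for n = 5, 6, 7. The R-squared needed for p<0.05 is pF/(pF + df):
- Joint, n=5: F(3,1) = 215.7, so 647.1/648.1 = 0.998.
- Joint, n=7: F(3,3) = 9.28, so 27.84/30.84 = 0.903.
- One index, n=5: F(1,3) = 10.13, so 10.13/13.13 = 0.771.
- One index, n=7: F(1,5) = 6.61, so 6.61/11.61 = 0.569.

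Simulated power at 5%, unadjusted, with one latent inflammation variable driving the gene and all three markers (100,000 runs):

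| Gene correlation | Joint n=5 | Index n=5 | Joint n=7 | Index n=7 |
|---|---|---|---|---|
| 0 (null) | 5% | 5% | 5% | 5% |
| 0.5 | 6% | 11% | 9% | 18% |
| 0.7 | 7% | 21% | 15% | 37% |
| 0.9 | 10% | 46% | 34% | 72% |

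**4. Rows are patients, markers tested separately, any one may decide.** For independent tests, 1 − 0.95³ = 14.3% of null genes pass at least one. With markers correlated as in step 3, simulation gives 12–13%.

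**5. All three visits, patient effects, three markers.** Residual df = 15 − 5 − 3 = 7 up to 21 − 7 − 3 = 11; with two visit effects, 5 to 9. This needs the markers at every draw and a within-patient model; the plan states neither.

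**6. A case against the index.** If only one of three independent markers carries the effect (r = 0.9, n = 7), power is about 20% for the index and 54% for the joint model.

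**The case against.** The strongest reply is that the plan does not commit to a three-predictor patient-level model. A reader might infer that it leaves 1–3 residual degrees of freedom outright. The documents do not support that: they describe per-cell measurement and give no model form, and a three-visit model would have more. That part of the reply stands, so the 1–3 figure is conditional.

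A reader might also infer that the joint fit floods the results with false biomarkers, because pure noise gives an average R-squared of 3/4 at n=5 and 3/6 at n=7. This does not follow either. The plan has no R-squared criterion; it names fold change, p-value and cell fraction. The joint F-test holds its 5% level. The genes entering this step also appear to be markers already extracted, not the whole panel. The patient-level joint model is weak, but its error rate is not inflated.

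The reply that this is a pilot seeking candidates also has force, and it supports a descriptive or exploratory label. It does not support the claim that the cell count makes 5–7 patients sufficient, nor p-values computed as if cells were independent.

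Finally, the choice of a composite index over another single summary is partly preference. The power comparison in step 3 suits an index by construction; step 6 shows the reverse case.

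**Conclusion.** The point holds in conditional form. The cell count cannot justify the number of patients for this regression, and no other section supplies the missing model.

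- **Cell-level rows**, the reading closest to the text: error control fails, with about 78–93% false positives per marker at 5,000 cells per patient and 42–79% at 500.
- **Patient-level joint fit for one contrast:** 1–3 residual df, correct 5% error, and low power (6–10% at n=5, 9–34% at n=7).
- **Separate tests with no deciding marker:** about 12–14% of null genes pass at least one.
- **A within-patient model over three visits:** less severe (5–11 df), but not stated.

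The false-positive figures rest on the assumed ICC, and the power figures on the assumed correlations and normal data. Neither can be checked from the documents. It would go too far to call the step worthless in both directions: with seven patients, a very strong association and no adjustment for the number of genes, power is not negligible. The change should be made, since it costs little and removes the worst reading.

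**What to change.** In section 6, Primary Outcomes, replace the regression sentence with wording that states:

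1. **Unit.** Expression is averaged per patient within each cell type. If all visits are used, it is averaged per sample and the model includes a patient effect.
2. **Contrast.** Whether baseline level, change from baseline or all visits is analysed, and at which draws CRP, ESR and procalcitonin are assayed.
3. **Regressor.** One inflammation measure, fixed before the sequencing data are seen; for example, the mean of the three log-transformed, standardised markers.
4. **Markers singly.** The three markers are shown separately in descriptive plots only.
5. **Status.** The step is exploratory, and the cell count is not offered as its justification.

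The cost is a few sentences of analysis wording, with no extra patients or sequencing.

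There are two downsides. An effect confined to one marker can be lost in the index (step 6), though the plots may still show it. The index also does not solve multiplicity: with Bonferroni over 20,000 genes, its simulated power at gene correlation 0.9 is below 0.1% for both n=5 and n=7. A restricted gene set or false-discovery control is a separate need.

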CBD biomarker extraction. We will contrast clusters of the same cell type at baseline (no CBD) and their counterparts after CBD administration. The difference in gene expression, measured in fold change, p-value, and ratio of cell fraction expressing the marker gene, will determine the phenotypic effect of CBD. For each cell type, we expect to extract one or more sets of CBD-specific candidate biomarkers that together will determine a phenotypic CBD per cluster (cell type) signature.

Investigational Product & Dosing Schedule. [name] (Co-I) will oversee CBD dosage and administration.We will source the investigational product from the same batch of our hemp-extract CBD product that is being used in the original protocol under IND 147985, 'Efficacy of a controlled short-term trial of Cannabidiol (CBD) ingestion on reducing symptomatic response and facilitating recovery after induced muscle injury' (Source: SunFlora, Inc, [name])''. SunFlora is a third-party tested hemp-derived product manufacturing company. SunFlora is dedicated to producing high quality hemp-derived products formulated to be safely used by the public and are manufactured in accordance with the Food and Drug Administration (FDA) Current Good Manufacturing Practices (cGMP) for Dietary Supplements, 21 CFR Part 111. Their hemp derived products are assessed multiple times at production process control points throughout the manufacturing process. Dietary ingredients used in the manufacturing process are accompanied by certificates of analyses (CoAs) confirming their identity and specifications. All finished products are tested to ensure they meet specifications prior to being released for distribution. The label and all labeling satisfy FDA requirements found under 21 CFR 101.

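### The primary gene scan treats cells rather than the 5 to 7 patients as the unit of evidence and states no error-rate rule; false discovery control alone would not repair cell-level p-values

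*Combined protocol and SAP*

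**What the plan says.** All references are to the combined protocol and SAP.

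- **Unit and sample size (section 6, Primary Outcomes).** The plan states that "we will measure RNA expression per single cell (not per patient" and that cells are pooled from all patients before clustering. It adds that "the number of patients (5-7) is sufficient to derive statistically viable results", "as we will collect 5,000 cells from each patient at each time point". It introduces this claim as holding from the single-cell viewpoint.
- **Scale (same paragraph).** "Each cell will be sequence individually to read the RNA expression from a panel of approximately 20,000 genes".
- **Contrast (section 6, CBD biomarker extraction).** "We will contrast clusters of the same cell type at baseline (no CBD) and their counterparts after CBD administration". The difference, "measured in fold change, p-value, and ratio of cell fraction expressing the marker gene, will determine the phenotypic effect of CBD". Primary Outcomes repeats the same three measures: "The difference in gene expression will be measured in fold change, p-value, and ratio of cell fraction expressing the marker gene".
- **Tests (section 6, Data analysis).** "The most informative gene expression markers will be identified by a host of non-parametric tests", with Kolmogorov-Smirnov as the example. That sentence concerns one cluster against other clusters. No test is tied explicitly to the before-after comparison.
- **Error rate.** No section gives an alpha, a cut-off for any of the three measures, or a multiplicity rule.
- **Hypothesis.** Sections 4 and 6 place the expected effect in monocytes through MAPK pathways, and section 5 makes MAPK-linked biomarkers the primary aim. The analysis text says only that MAPK genes are expected to change strongly.

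**The concern.** There are two linked problems. First, a screen of thousands of genes with no stated error rate gives a list in which chance entries cannot be counted. Second, the sample is justified by counting cells. CBD is given to patients, and each patient contributes one blood sample per visit. Anything that shifts a whole sample between visits (an intercurrent infection, sample handling, a sequencing batch) moves all its cells together. A test over cells reads that shift as a precise treatment effect.

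The list is the declared primary outcome, and sections 5 and 7 say the data are meant to inform larger studies. False candidates would be carried forward. A natural first remedy, adding false discovery control, works only if the p-values going into it are valid.

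**Working it through.** **1. The plan's own figure.** Patients × time points × cells: 5 × 3 × 5,000 = 75,000 and 7 × 3 × 5,000 = 105,000. Both match the plan. They count cells; the independent units remain 5 to 7. There is no power calculation to reproduce.

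**2. Missing error rate, even with valid p-values.** Expected chance findings = genes × alpha, if no gene changes. For one cell type and one contrast with 20,000 genes: 1,000 at 0.05, 200 at 0.01, 20 at 0.001. If only a quarter of genes (5,000) survive quality control: 250, 50 and 5. These are upper bounds, because fold-change and cell-fraction cut-offs, once stated, would lower them.

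**3. Cells as the unit.** Inputs not in the plan and therefore assumed: *m*, the cells of one type per sample (100 or 500, that is 2% or 10% of 5,000), and ICC, the share of variance specific to a patient at a visit (0.001 to 0.05). Total variance is set to 1. If cells are treated as independent, the variance of the baseline-versus-later difference is understated by the factor DE = 1 + (*m* − 1) × ICC. A nominal two-sided 5% test then has real type I error 2 × [1 − Φ(1.96/√DE)]. The last column is a null simulation: N = 5, 20,000 unchanged genes, pooled cell-level z-test, Benjamini-Hochberg at 5%, mean of 20 runs, range over repeat simulations.

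| Cells *m* | ICC | DE | Real type I error | Null genes passing BH 5% |
|---|---|---|---|---|
| 100 | 0.001 | 1.10 | 6% | 0 to 1 |
| 500 | 0.001 | 1.50 | 11% | 13 to 22 |
| 100 | 0.01 | 1.99 | 16.5% | 360 to 395 |
| 500 | 0.01 | 5.99 | 42% | about 6,500 |
| 500 | 0.05 | 25.95 | 70% | about 13,500 |

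The number of patients does not enter DE, so N = 7 gives much the same: about 375 to 390 (100 cells, ICC 0.01) and about 13,550 (500 cells, ICC 0.05). With 5,000 testable genes at N = 5 these two settings pass 84 and 3,387.

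**4. Patients as the unit.** Paired t-tests on patient means from the same simulated data, followed by Benjamini-Hochberg, pass 0 genes in nearly all runs and never more than 2.

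**5. What the correction costs in yield.** Assume genes truly change by 2 SD (SD of the within-patient change), tested from baseline to month 2 with Benjamini-Hochberg at 5% over 20,000 genes. The three-visit model has patient and visit effects, with residual df 2(N − 1) = 8 or 12. It assumes equal, independent within-patient errors and was simulated with the same change at both follow-ups.

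| Genes changed | Model | Found, N = 5 | Found, N = 7 |
|---|---|---|---|
| 1,000 | two-visit paired t | 0.1 to 0.2% | 47% |
| 1,000 | three-visit | about 42% | about 89% |
| 200 | two-visit paired t | about 0% | about 3% |
| 200 | three-visit | about 5% | about 63% |

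**6. One prespecified score.** Two-sided 0.05, 80% power, noncentral t with noncentrality *d*√N. With two visits (df 4 or 6), *d* = 1.68 at N = 5 and 1.27 at N = 7. With three visits (df 8 or 12), *d* = 1.43 and 1.15.

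**The case against.** The strongest defence is that this is a pilot. The plan uses that word, speaks of candidate biomarkers and preliminary data, and no efficacy decision follows. It never commits to a cell-level test for the before-after contrast, and its sufficiency claim carries a single-cell qualifier. The size of the inflation depends wholly on assumed ICC and cell counts, and at ICC 0.001 it is small.

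Much of this stands. Exploratory screening is legitimate. A reader might infer that the final gene list will be mostly noise, or that five patients make the study worthless. The documents support neither: they give no ICC or cell counts, and the computed range starts at zero. What does not stand is the qualifier as a defence. The claim concerns statistical sufficiency for an effect of CBD, and more cells per patient cannot supply it.

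Three other stronger readings also fail.

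- **That the MAPK hypothesis has no time point at all.** Section 5 speaks of samples before and after two months of CBD. What is missing is a ranking of month 1 against month 2 in section 6, and a gene set and statistic.
- **That no test could apply to the before-after contrast.** The cluster-comparison tests appear just before it and may have been intended. The text is ambiguous.
- **That a corrected scan must be nearly empty at N = 5.** That holds for the two-visit paired t-test, but the three-visit model can do far better under its assumptions.

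**Conclusion.** The concern holds for the unit of analysis and the missing error rate, and both should be settled before the data are analysed because they govern the primary outcome. The sufficiency sentence is wrong as written: cell count does not replace patient count. If testing follows that logic, false discovery control at 5% passes hundreds to over 13,000 of 20,000 unchanged genes for ICC 0.01 to 0.05, and about 0 to 22 for ICC 0.001. These counts rest on the assumed ICC, 100 or 500 cells per type and sample, and a pooled z-test that ignores patient and sample. That the plan would use such a test is inferred from its stated unit and its justification of sample size; it is not written out.

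The absence of a prespecified MAPK gene set and statistic is a real but secondary gap. The regression on inflammation markers is a minor wording matter: it refers to variation in baseline inflammation and is followed by a sentence fragment, where change after CBD was probably meant.

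**What to change.** 1. **Patient as the independent unit.** Run the before-after contrasts on pseudobulk values per patient, visit and cell type with a paired or three-visit model, or on cells with a mixed model that has patient and sample effects and small-sample degrees of freedom. Apply Benjamini-Hochberg within each cell type and contrast. Label the output as hypothesis-generating candidates. Replace the sufficiency sentence with a statement that patients, not cells, are the independent units.
2. **MAPK score (secondary).** Before sequencing data are seen, fix one gene-set score, for example the count-fraction method used for the preliminary mouse data in section 3 applied to a named public MAPK set. Test it from baseline to month 2 in monocytes at patient level. Report the other cell types alongside, since section 4 asks which population is affected. The choice of a single monocyte score is partly a matter of judgement; what matters is that it is fixed in advance.
3. **Regression wording (minor, separate).** State it as within-patient change in expression against within-patient change in C-reactive protein, erythrocyte sedimentation rate and procalcitonin.

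**Cost.** No additional patients, visits or sequencing; analysis wording and one gene set chosen in advance. The gene list will be shorter, by an amount that depends on the model (step 5 of the working), so the model should be named now. The MAPK score detects only large changes, so a null result will be weak evidence against the hypothesis, and the plan should say so.

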The main objective of this project will be to identify inflammatory reduction biomarkers linked to MAPK-dependent alterations after CBD administration, as well as other systemic effects on cell signaling pathways. Investigating the role of cell-specific biomarkers describing the molecular response to CBD-administration may open avenues for additional therapeutic strategies that can help reduce the burden of chronic musculoskeletal pain and other pain-related symptoms and comorbidities in people living with HIV (PLWH). The team proposes to study the effects of CBD on inflammation and chronic pain in PLWH by enrolling five persons with HIV who will provide blood samples before and after taking CBD for two months. In the process, the goal will be to establish the molecular role(s) of different immune cells using single cell RNA-sequencing. Preliminary data from this study are expected to pave the way for further investigations in larger clinical cohorts. The primary aim of this project will be to identify key inflammatory reduction biomarkers linked to MAPK-dependent alterations after CBD administration. Secondary outcomes include pain relief and reductions in pain-related symptoms. We will use a prospective pilot study design where patients will self-administer the investigational product (CBD-extract) for 60-days (2 months).

Specific Aim #1 – Determine the effects of CBD on chronic on quality of life in PLWH. We will compareQuality of Life (QoL) measures between treatment conditions, including pain and pain-related symptoms, if present.

Specific Aim #2 – Determine key biobehavioral mechanisms contributing to antiinflammatory and analgesic effects of CBD administration in PLWH. We hypothesize that change in molecular (alterations in cell signaling and reduction in inflammatory cytokines), psychological (reduction in pain-related fear and pain catastrophizing), and pain sensitivity regulation measures will be associated with pain relief, inflammation reduction, and reservoir shrinkage. We will quantify the shift in anti-inflammatory macrophage/monocyte population caused by CDB administration by examining gene expression at the single-cell level from the PBMC samples. This will allow us to accurately pinpoint gene under- or over-expression patterns at the RNA level (biomarkers), that are both induced by CBD administration in PLWH, and specific to different cells (e.g., monocytes, T cells, B cells, or other immune cells).

6. Research Plan

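### The plan claims cell-type-specific biomarker genes, but no planned analysis compares the change after CBD between cell types

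*Combined protocol and SAP*

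**What the plan says.** Section 6, Primary Outcomes, states of the CBD-related marker genes: "These biomarker gene will be unique for each cell type". It adds that the study should show CBD acting differently on different immune cells. Section 5, Specific Aim #2, seeks expression patterns that are both induced by CBD and "specific to different cells". The Background asks in which cell population MAPK signalling is disturbed, which is a question about differences between populations.

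The analysis is in section 6, CBD biomarker extraction: "We will contrast clusters of the same cell type at baseline (no CBD) and their counterparts after CBD administration". The yardsticks, repeated under Primary Outcomes, are: "The difference in gene expression will be measured in fold change, p-value, and ratio of cell fraction expressing the marker gene". No threshold is attached to any of them. The product is one or more gene lists per type: "For each cell type, we expect to extract one or more sets of CBD-specific candidate biomarkers".

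Clusters are compared with each other only under Data analysis, where marker genes are found by "comparing a given cluster against either a nearby cluster or all other clusters". That step serves to name the clusters.

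**The concern.** Specificity is a statement about a difference: the change in monocytes, say, is not the change in T cells. Separate before-after tests do not estimate that difference. A gene can pass in one type and miss in another because the second type has fewer cells, noisier counts or an unlucky draw, while the underlying change is the same in both.

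Cell-type signatures are the main product of the study and are meant to inform larger cohorts. If specificity is read off from which lists a gene appears in, some genes will be carried forward under the wrong label. Under cell-level testing the abundant types have more power and would collect more of the apparently specific genes.

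**Working it through.** **1. The plan's own figure.** Patients × time points × cells per sample: 5 × 3 × 5,000 = 75,000 and 7 × 3 × 5,000 = 105,000. Both ends of the stated range reproduce. The plan gives no significance level, effect size, power or cut-off for the biomarker analysis, so every percentage below rests on assumptions.

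**2. Which planned analyses could support specificity?**
- The within-type contrast (CBD biomarker extraction) asks whether a gene changed in type A. It says nothing about A minus B.
- The cluster-against-cluster tests (Data analysis) compare expression levels to annotate cell types, not the response to CBD.
- The regression on C-reactive protein, sedimentation rate and procalcitonin (Primary Outcomes) relates genes to inflammation, not to differences between types.

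There is also no rule for overlapping lists and no numerical criterion for unique.

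**3. Simple illustration.** Take a gene with the same true change in the three types the plan names (B cells, T cells, monocytes). Assume power p in each type and independent results.

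P(exactly one) = 3p(1−p)²; P(at least one) = 1 − (1−p)³.

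| p | exactly one | at least one | share called in one type only |
|---|---|---|---|
| 0.2 | 0.384 | 0.488 | 79% |
| 0.3 | 0.441 | 0.657 | 67% |
| 0.5 | 0.375 | 0.875 | 43% |
| 0.8 | 0.096 | 0.992 | 10% |

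**4. Patients as units.** Assume a paired t test per type, two-sided 0.05, with power from the noncentral t distribution (n − 1 degrees of freedom, noncentrality d√n). With n = 5 and standardised change d = 0.5, 1.0, 1.5 and 2.0, power is 0.141, 0.401, 0.711 and 0.909. The same formula gives one-type-only shares among called genes of 85%, 55%, 18% and 2%. With n = 7 they are 79%, 31%, 2% and 0%. Correlation between types matters: at n = 5 and d = 1.0, simulation gives 55% at correlation 0, about 45% at 0.5 and 33% at 0.8.

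**5. Cells as units, as Primary Outcomes proposes.** Assume 5 patients, two-sided z tests at 0.05/20,000, and shares of T cells 60%, monocytes 20% and B cells 10%. Cells per type per visit are m = 25,000 × share, and z = effect/√(2/m). For a shared effect of 0.10 SD, m = 15,000, 5,000 and 2,500, and power is 1.00, 0.615 and 0.12. P(one type only) = 1.00 × 0.385 × 0.88 = 34%, practically all of it in T cells. At 0.05, 0.15 and 0.20 SD the figures are 36%, 0.1% and 0%. With equal thirds, the 0.10 SD figure is only 0.5%, so the unequal cell numbers drive that result.

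**6. A direct test.** In simulation, a paired test of the difference in change between two types called a fully shared response different about 5% of the time (4.9% to 5.2%) at every effect size tried, for n = 5 and n = 7.

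**The case against.** The strongest reply is that unique may mean only that each type receives its own signature, in which genes may recur. The description of the output under CBD biomarker extraction supports that reading. No passage says that overlapping genes are dropped, or that passing in one type only makes a gene exclusive to it. This stands. A reader might infer that shared responses *will* be mislabelled as a matter of course, but the documents do not support that. A strong shared effect would pass in several types and show as overlapping lists, as steps 4 and 5 confirm.

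A reader might also infer that the plan contradicts itself, because Motivation to study single cells says "We hypothesize CBD-alterations to reverberate along the whole immune-modulation system through cellular cross-talk". It does not. The same paragraph allows that different cell types may show their own CBD-induced phenotypes, and a pathway such as MAPK can be altered overall through different genes in different types. What that hypothesis does show is that shared responses are plausible here.

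It is also fair to say that this is a pilot producing candidate markers, and that the size of the problem depends on assumed power and independence. Both points lower the severity. Neither supplies the missing comparison: under either reading of unique, Specific Aim #2 still promises specificity that no planned analysis tests.

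**Conclusion.** The gap is real. Specificity is asserted in advance and nothing planned can support it, so genes with similar responses in several types can be reported as specific to one. The risk is substantial when per-type power is low to moderate: 43% to 79% of called genes at power 0.5 down to 0.2, with three types, equal power and independence all assumed. It is small for strong effects (10% at power 0.8), lower when types are positively correlated, and higher when cell numbers are unequal. It would be going too far to say that the signatures would mostly reflect which type happened to pass, since that depends on effect sizes the documents do not give. Participants and data collection are unaffected. This should be fixed before the data are analysed.

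**What to change.** - Delete the uniqueness sentence under Primary Outcomes, or state that it means a separate signature per type in which genes may overlap.
- For each gene, aggregate counts by patient, visit and cell type. Test the cell-type-by-visit difference in within-patient change, with patient as block and control for multiplicity.
- Call a gene cell-type-specific only if that test passes. Report other responding genes as *specificity not shown*, with the estimated change and interval in every cell type. Do not label them shared: a non-significant interaction is no more proof of sameness than a missed within-type test is proof of difference.

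The samples and sequencing are already planned, so the cost is a few sentences and modest extra analysis. Cells from the same blood sample are compared, so shifts common to all types cancel.

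The downside is low power. Suppose a gene changes by 1.0 SD in one type and not at all in another, with independent changes of equal variance. The standardised difference is 1/√2 = 0.71, and a paired test at 0.05 has about 23% power with 5 patients and 35% with 7. At 0.05/20,000 power is practically nil. Few genes will earn the label, and specificity claims should be described as exploratory.
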